9.10.4 Vital signs and body weight

The following summary displays are provided by treatment group, all based on the SAF:

- Blood pressure and body weight including absolute change from baseline, as described in Section 5.5.10, are summarized, by parameter and visit. Except for 'Baseline', 'Last on treatment', 'Day-15 follow-up' and 'Day-30 follow-up', only treatment-emergent results from nominal scheduled visits are included; premature EOT visit is mapped to a scheduled visit [see Section 11.3]. These are summarized descriptively and mean changes (with standard error) from baseline in blood pressure are also presented graphically over time (plots starting with zero change at baseline);

- Blood pressure including absolute change from baseline on Day 1, by time point (pre-dose, 1–12 hours post dose), are summarized descriptively and mean changes (with standard error) from pre-dose are also presented graphically over time (plots starting with zero change at pre-dose);
- Descriptive summary statistics of blood pressure including absolute change from pre-dose on Day 1 of first Re-initiation, by time point (pre-dose, 1–12 hours post dose); Note: Data from re-initiations beyond the first are listed only;
- Number and percentage of subjects with any treatment-emergent blood pressure result meeting the criteria defined in Section 5.5.10.1. Percentages are based on the number of subjects with at least one treatment-emergent result available for the corresponding parameter;
- Number and percentage of subjects with post-dose blood pressure result on Day 1 and Day 1 of any re-initiation meeting the criteria defined in Section 5.5.10.1 are presented overall post-dose hours and by individual time point. Percentages are based on the number of subjects with blood pressure results available for the corresponding parameter and timepoint;

All blood pressure and body weight results are listed by treatment group and visit based on the SCR. Qualitative results ('normal' or 'abnormal') of body temperature and pulse rate are listed as collected in the eCRF, by treatment group and visit based on the SCR.

9.10.5 Laboratory tests

Descriptive summary statistics by visit (including protocol-mandated between visit assessments) and treatment group are provided for laboratory test results reported by the central laboratory and corresponding absolute changes from baseline, based on the SAF. Except for 'Baseline', 'Last on treatment', 'Day-15 follow-up' and 'Day-30 follow-up', only treatment-emergent results from nominal scheduled visits are included; premature EOT visit is mapped to a scheduled visit [see Section 11.3]. Data are displayed in SI units as provided by the central laboratory. In the same manner, mean absolute changes from baseline with their standard error are presented graphically (plots starting with zero change at baseline). Values from unscheduled visits are not included in by visit summaries but are included in the listings and in the summaries for marked abnormalities and liver function test abnormalities.

For lymphocyte counts, this table and plot are also provided on percent changes from baseline. The number of subjects with at least one treatment-emergent marked laboratory abnormality is summarized by treatment group, based on the SAF. The worst case in each direction is considered and summarized in all applicable categories, i.e., a subject counted in LLL is also counted in LL for a given parameter; also, a subject maybe counted in both the high and the low category for a given parameter. In addition, the number of subjects with treatment-emergent liver function test abnormalities is summarized by treatment

group. This tabulation is also repeated for abnormalities that occurred after start of study drug and up to and including EOT + 1 day. The denominator for percentages is the number of subjects with at least one post-baseline assessment.

A plot to evaluate Drug-Induced Serious Hepatotoxicity (eDISH plot) is provided based on the highest observed treatment-emergent ALT and total bilirubin values, considering both, central and local laboratory data. Individual subject's values expressed as \times ULN are plotted on a log-log scatter plot (ALT on the horizontal axis, total bilirubin on the vertical axis); reference lines are drawn at Hy's law thresholds, i.e., at $3 \times$ ULN for ALT and at $2 \times$ ULN for total bilirubin. A footnote is presenting, for each treatment group, the number and percentage of subjects falling in each of the 4 quadrants defined by these reference lines. This eDISH plot is repeated for abnormalities that occurred after start of study drug and up to and including EOT + 1 day.

Safety laboratory hematology, clinical chemistry, urinalysis parameters planned as per protocol are also presented in subject data listings based on the SCR. All abnormalities and marked abnormalities including those at baseline are flagged in the listings.

Other laboratory parameters are presented in a separate listing on the SCR.

Further analyses related to lymphocytes are described in Section 9.13.

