A safety assessment (ECG, vital signs, laboratory) is considered treatment-emergent, if the assessment date is on or after the study treatment start date and prior to or on the study treatment end date + 15 days (inclusive). If both, the assessment date/time and the date/time of study treatment start are available, only events with date/time on or after the date/time of study treatment start are considered to be treatment emergent. In case of (partially) missing assessment dates/times, or for assessments on treatment Day 1 with reported assessment time contradicting the time point label, the nominal visit and time point labels will be used to determine whether an assessment is considered as treatment-emergent or not. For example, a blood pressure measurement with an assessment date on Day 1 but a missing assessment time or an assessment time after the time of first study drug intake, will not be considered treatment emergent if reported under the time-point “Pre-dose” in the eCRF, however it will be considered if reported as “2 hours post-dose” in the eCRF.

A safety event (AE, SAE, Death) is considered treatment-emergent if the onset date/date of occurrence is on or after the study treatment start date and prior to or on the EOT date + 15 days (inclusive). Missing or partially missing onset or occurrence dates are imputed as described in Section 12.3. If both the onset/occurrence date/time and the date/time of study treatment start are available, only events with date/time on or after the date/time of study treatment start are considered to be treatment emergent.

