5.5.11.2 Qualitative ECG variables

Morphological ECG findings are reported by the central reader, and mapped to CDISC standard (codelist C71150, with high level categories from codelist C71152) in the SDTM.

For analyses in tables the following categories are anticipated:

- Atrioventricular Conduction
- Axis and Voltage
- Chamber Hypertrophy or Enlargement
- Conduction
- Ectopy
- Intraventricular-Intraatrial Conduction
- Rhythm Not Otherwise Specified
- ST Segment, T wave, and U wave
- Sinus Node Rhythms and Arrhythmias
- Supraventricular Arrhythmias
- Supraventricular Tachyarrhythmias
- Ventricular Arrhythmias

Findings related to interpretation or technical issues are only included in listings.

Morphological ECG findings are flagged as “New” if not present at any pre-treatment assessment (i.e. at any ECG assessed prior to the study treatment start) or “Pre-existing” if present at any pre-treatment assessment. In case of missing or non-evaluable pre-

treatment ECG assessment, it is conservatively assumed that any treatment-emergent morphological ECG finding is “New”.

For presentation of these findings in by-visit and by-hour tables, all reported abnormalities are considered in case of multiple assessments available at a visit or visit/timepoint.

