5.5.12.1 Derivations

Numerical results are converted into both conventional and SI units as per QS document OTH-000005 (Definition of Marked Abnormalities in Laboratory Data). Results reported as below the lower limit of quantification (LLOQ) are set to the LLOQ value. Results reported as $> XX$ are set to XX for calculation of summary statistics. For all quantitative safety laboratory data, baseline, last on-treatment, Day-15 follow-up, Day-30 follow-up, last follow-up assessment is flagged and absolute change from baseline and percent changes from baseline are calculated for each post-baseline value, as described in Section 5.5.1.

Flags are derived according to project specific ranges for marked laboratory abnormalities as documented in the protocol [see Appendix D]. Marked laboratory abnormalities are labeled to indicate the increasing severity of abnormally low (“LL”, “LLL”), or high values (“HH”, and “HHH”) for each of the laboratory parameter listed. For INR, the general range specified in the protocol is applied to all subjects irrespective of concomitant treatment with anticoagulants.

The following flags will be derived for Alanine aminotransferase (ALT), Aspartate aminotransferase (AST), Total bilirubin (TBIL), and Alkaline phosphatase (ALP):

- ALT: $\geq 1 \times \text{ULN}$, $\geq 3 \times \text{ULN}$, $\geq 5 \times \text{ULN}$, $\geq 8 \times \text{ULN}$, $\geq 10 \times \text{ULN}$, $\geq 20 \times \text{ULN}$
- AST: $\geq 1 \times \text{ULN}$, $\geq 3 \times \text{ULN}$, $\geq 5 \times \text{ULN}$, $\geq 8 \times \text{ULN}$, $\geq 10 \times \text{ULN}$, $\geq 20 \times \text{ULN}$
- ALT or AST: $\geq 3 \times \text{ULN}$, $\geq 5 \times \text{ULN}$, $\geq 8 \times \text{ULN}$, $\geq 10 \times \text{ULN}$, $\geq 20 \times \text{ULN}$
- TBIL $\geq 2 \times \text{ULN}$
- ALT or AST $\geq 3 \times \text{ULN}$ and TBIL $\geq 2 \times \text{ULN}$ (at the same sample date)
- ALT or AST $\geq 3 \times \text{ULN}$ and TBIL $\geq 2 \times \text{ULN} + \text{AP} < 2 \times \text{ULN}$ (at the same sample date)
- INR > 1.5 combined with ALT or AST $\geq 3 \text{ ULN}$ (at the same sample date).

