9.10.8.1 Columbia Suicide ideation or behavior

Suicidal Ideation, Suicidal Behavior or Self-Injurious Behavior without Suicidal Intent will be listed for each patient, at each assessment visit on the SAF. Events occurring during the period up to EOT + 15 days (treatment-emergent period) will be flagged.

Number (%) of subjects with suicidal ideation (overall and by category), suicidal behavior (overall and by category), suicidal ideation score ≥ 4 or suicidal behavior and/or self-injurious behavior without suicidal intent will be tabulated by treatment group and visit, as well as up to EOT + 15 days (worst outcome). Analyses will be based on subjects in the SAF who have at least one eC-SSRS measurement during the respective visit or period available. The analysis will be repeated in the subgroup of patients with no baseline result available.

For subjects who have in addition a baseline eC-SSRS assessment available shifts from baseline (maximum score from pre-treatment recent history) to the worst reported outcome (the maximum score) up to EOT + 15 days will be tabulated by treatment group to demonstrate any changes in Suicidal Ideation and Suicidal Behavior score categories.

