As per protocol, WBC and total lymphocyte counts will be assessed every 4 weeks up to Week 24 (i.e., there are 3 protocol mandated between-visit assessments for those tests at Week 8, Week 16, and Week 20 when no regular visit is scheduled). Likewise, liver tests (ALT, AST, INR, alkaline phosphatase and total bilirubin) will be assessed in-between visits at Weeks 6, 8, 10, 14, 16, 18, 20, and 22 in all countries except Canada, the United States, and Mexico. In Canada, the United States, and Mexico there are only 3 protocol mandated between-visit assessments for the liver function tests at Week 8, Week 16, and Week 20.

These assessments are considered scheduled and are included in corresponding by-visit tabulations labeled as follows:

- Additional Visit - Week 6
- Additional Visit - Week 8
- Additional Visit - Week 10
- Additional Visit - Week 14
- Additional Visit - Week 16
- Additional Visit - Week 18
- Additional Visit - Week 20
- Additional Visit - Week 22

Visit-based efficacy, quality of life or pharmaco-economic assessments are summarized according to the nominal visit up to EOS, irrespective if conducted during PTO or not:

- Baseline (Derived)
- Visit 6 - Week 12
- Visit 7 - Week 24
- Visit 8 - Week 36
- Visit 9 - Week 48
- Visit 10 - Week 60
- Visit 11 - Week 72
- Visit 12 - Week 84
- Visit 13 - Week 96
- Visit 14 - Week 108

Premature EOT visits are mapped to and summarized within a scheduled visit following the window approach described in Section 11.3; they will not be summarized as “Visit 14 - Week 108” unless they are mapped to this visit as per approach described in Section 11.3.

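### Laboratory abnormalities are called treatment-emergent by sample date, so cases already present at baseline are counted with new ones, and SAP 9.10.5 describes no categorical new-onset or shift summary

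*SAP*

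**What the plan says.** Section 5.5.1 gives one timing rule for ECG, vital signs and laboratory assessments. A result is treatment-emergent if "the assessment date is on or after the study treatment start date and prior to or on the study treatment end date" plus 15 days. Baseline status plays no part.

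Section 5.5.12.1 sets the laboratory categories. Marked abnormalities (LL, LLL, HH, HHH) follow the ranges in Appendix D, Table 13. Liver categories are multiples of ULN, introduced by "The following flags will be derived for Alanine aminotransferase (ALT), Aspartate aminotransferase (AST" and others, and they start at 1 x ULN for ALT and for AST.

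Section 9.10.5 then reports, by arm, the "number of subjects with at least one treatment-emergent marked laboratory abnormality is summarized by treatment group", and likewise the liver-test abnormalities, with the liver table repeated up to EOT + 1 day. On percentages it says: "The denominator for percentages is the number of subjects with at least one post-baseline assessment".

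Baseline enters the laboratory reporting in these places:
- by-visit absolute changes from baseline, with percent changes and further displays for lymphocytes (9.10.5, 9.13);
- the listings: "All abnormalities and marked abnormalities including those at baseline are flagged in the listings";
- Table 13: when baseline haemoglobin is above ULN, HH or HHH requires a rise from baseline; creatinine has an alternative criterion relative to baseline.

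**The concern.** A table headed treatment-emergent is normally read as showing what arose on treatment. Under the rules above, a subject whose cholesterol is 8.0 mmol/L at baseline and stays there is counted as a treatment-emergent HH case, because the limit is 7.75 mmol/L. A subject whose ALT was already at or above 1 x ULN before the first dose is counted in that liver category if it is seen again.

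At stake is how a descriptive incidence is read. Pre-existing values add to the percentage in each arm, and no summary described in 9.10.5 lets the reader take them out again.

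**Working it through.** **Does any described display separate new from pre-existing cases?**

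| Domain | What the SAP describes | Separates or relates to baseline by category? |
|---|---|---|
| ECG morphology (5.5.11.2, 9.10.3) | findings marked New or Pre-existing | yes |
| eC-SSRS (9.10.8.1) | shift from baseline "to the worst reported outcome (the maximum score) up to EOT + 15 days will be tabulated by treatment group" | yes |
| Blood pressure (5.5.10.1) | absolute limits, plus changes of 20 or 15 mmHg | yes, beside the absolute limits |
| QTc, PR (5.5.11.1) | absolute QTc limits, plus QTc increases over 30 and 60 ms; PR over 200 ms with a rise over 20 ms | yes |
| Spirometry (5.5.13.1) | falls from baseline, reversibility | yes |
| Laboratory (9.10.5) | counts in Table 13 and ULN categories | only through the haemoglobin and creatinine rules |

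The haemoglobin rule stops an unchanged high value from counting. The creatinine rule is joined by *or*, so it adds cases and removes none. By-visit means do not show movement between categories, and they leave out unscheduled samples, which the abnormality tables include. Listing flags would have to be tallied by hand.

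**How large could the effect be?** The SAP gives no baseline prevalence and no incidence, so there is no figure to reproduce. The following is an illustration on assumed inputs:
- p0 = share of subjects in the category at baseline (assumed 1%, 5%, 10%);
- r = chance that such a subject is in the category again in the window (assumed 0.5 to 1.0);
- new = true new-onset rate among the others (assumed).

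Reported percentage = p0 x r + (1 - p0) x new. 
Rise over new = p0 x (r - new). 
Reported risk difference, with the same p0 and r in both arms = (1 - p0) x (new_A - new_B), whatever r is.

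With p0 = 5%:

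| new, A vs B | r = 0.5 | r = 1.0 | Risk difference |
|---|---|---|---|
| 6% vs 2% | 8.2% vs 4.4% (rise 2.2, 2.4) | 10.7% vs 6.9% (rise 4.7, 4.9) | 3.8 (true 4.0) |
| 30% vs 20% | 31.0% vs 21.5% (rise 1.0, 1.5) | 33.5% vs 24.0% (rise 3.5, 4.0) | 9.5 (true 10.0) |

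Worked cell: 0.05 x 0.5 + 0.95 x 0.06 = 0.025 + 0.057 = 0.082. The ratio for 30% vs 20% would go from 1.50 to 1.44 (r = 0.5) or 1.40 (r = 1.0), but no ratio is planned for this table.

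Pre-existing cases per arm, with 1133 / 2 = 566.5 subjects: 566.5 x p0 x r = 2.8 to 5.7 at p0 = 1%, 14.2 to 28.3 at 5%, and 28.3 to 56.7 at 10%.

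**Is a high r plausible?** A completer has 11 scheduled post-baseline chemistry samples (Weeks 2, 4, 12, 24, 36, 48, 60, 72, 84, 96, 108). On the additional liver tests, section 11.4 says that they "will be assessed in-between visits at Weeks 6, 8, 10, 14, 16, 18, 20, and 22 in all countries". Sites in the US, Mexico and Canada are exempt from this and take only three extra samples. That makes 11 + 8 = 19 liver samples in general, against 11 + 3 = 14 at the exempt sites. If each sample had an assumed 10% chance of repeating the abnormality, independently, r = 1 - 0.9^k, which is 0.686 for k = 11, 0.771 for k = 14 and 0.865 for k = 19. Within-subject correlation would lower these values.

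**The case against.** The strongest reply is that this is a stated convention, not an error. Section 5.5.1 defines the term once and the SAP applies it consistently, including to absolute limits for blood pressure, heart rate and QTcF. A reader might infer a contradiction from the different handling of ECG morphology and eC-SSRS, but there is none. Those are a qualitative reading and an instrument that collects history by design, and for eC-SSRS the shift table stands beside an unconditioned count. That part of the reply stands. It does not show that the laboratory categories need no such companion table.

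A reader might also infer that the SAP has no baseline-aware laboratory display at all. It does not support that: change-from-baseline summaries, lymphocyte displays, listing flags and the haemoglobin rule all use baseline. The gap is narrower, namely a categorical summary that separates new from pre-existing cases.

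Three further limits stand:
- Section 13 places the table list in a separate file, so a shift table may exist there.
- The entry criteria on haematology, liver, renal function and poorly controlled diabetes, as named in the deviation code list, probably keep many marked values rare at baseline. Their laboratory thresholds are not shown.
- All inputs to the illustration are assumed, so it shows the mechanism and is no evidence of actual size.

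**Conclusion.** The point holds as a low-priority improvement. Except for high haemoglobin when baseline exceeds ULN, the counts in 9.10.5 mix pre-existing with new cases under a treatment-emergent label, and the section describes no categorical summary that separates them. The effect is raised descriptive percentages in both arms, probably concentrated in cholesterol, triglycerides and ALT or AST at or above 1 x ULN. The actual size cannot be computed from the SAP.

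A reader might infer that one treatment is made to look better or worse. The documents do not support that. Randomization should balance pre-existing cases, the risk difference shrinks only by the factor 1 - p0, and no test or ratio is attached to the table. Nor is there reason to expect a material effect at ALT or AST of 3 x ULN and above, where baseline prevalence is probably near zero; this rests on entry limits whose values are not given here.

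**What to change.** In 9.10.5, for marked abnormalities and liver-test categories (including the EOT + 1 day repeat):

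1. Keep the present count, relabelled *any abnormality in the treatment window*. It must stay, because a new-onset count alone misses worsening within a category: triglycerides rising from 3.5 to 11.0 mmol/L remain HH (above 3.42) and do not reach HHH (above 11.4).
2. Add either a baseline-to-worst shift table by parameter, as 9.10.8.1 does for eC-SSRS, or a second column counting only subjects who were not in that category or a worse one at baseline, with those subjects as denominator.
3. Leave the haemoglobin rule unchanged, and still count creatinine above 1.5 x baseline.
4. Treat a missing baseline as not abnormal. This follows 5.5.11.2, where with no evaluable pre-treatment ECG "it is conservatively assumed that any treatment-emergent morphological ECG finding" is new.

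The cost is modest programming. The second column needs denominators by parameter, direction and category, plus the exceptions above; the shift table is simpler. Section 5.5.12.1 already flags baseline for all quantitative safety laboratory data, so no new data are needed. If the separate table list already holds a shift table, a reference to it in 9.10.5 and the new label are enough.

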9.10.6 Pulmonary function tests - Spirometry

The following summary displays are provided by treatment group, all based on the SAF:

- Treatment-emergent FEV1, FVC, FEV1/FVC, %FEV1, and %FVC including absolute and percent change from baseline, as described in Section 5.5.13.1, are summarized, by parameter and visit. Except for 'Baseline', 'Last on treatment', 'Day-15 follow-up' and 'Day-30 follow-up', only treatment-emergent results from nominal scheduled visits are included; premature EOT visit is mapped to a scheduled visit [see Section 11.3]. These are summarized descriptively and mean changes from baseline are also presented graphically with their standard error over time (plots starting with zero change at baseline).
- A scatter plot of all measured treatment-emergent %FEV1 values is provided. Treatment groups are color-coded and linear regression lines (with time as explanatory variable) are drawn per treatment group. These regression lines are to visualize the course over time after an initial change in pulmonary function and for that reason, exclude measurements taken prior to study day 26. The regression equation is given in a footnote.
- Number and percentage of subjects with any occasion of treatment-emergent low spirometry values as defined in Section 5.5.13.1 are presented. Percentages are based on the number of subjects with at least one treatment-emergent result available for the corresponding parameter;

- In the subset of subjects experiencing a decrease of ≥ 200 mL or $\geq 12\%$ in FEV1 (or FVC) from baseline to the last assessment on treatment, the number and percentage of subjects with the condition reversed, not reversed, or missing data on reversibility at the last follow-up result is provided;
- FEV1, FVC, FEV1/FVC, %FEV1, %FVC at the following three time points (for definition, see Section 5.5.1) are displayed graphically by box-and-whisker plots visualizing mean, median, interquartile ranges, SD, and outliers over time: Baseline, last assessment on treatment, and Day-15 follow-up assessment. All subjects with data available at all three time points are included. A corresponding table is included as well.
- Individual absolute change from baseline to last assessment on treatment versus absolute change from baseline to last follow-up assessment is graphically displayed for FEV1, FVC, %FEV1, and %FVC by means of scatterplots with treatment groups color-coded.

All spirometry results (best effort results) are listed by treatment group and visit based on the SCR.

